3.12.2 The period following the hospital discharge until the 30th postoperative day

The researcher will contact the liver transplant recipient on alternate days by telephone to detect any signs and symptoms of SSI. Also, the surgical wound will be evaluated every 7 days during the ambulatory doctor's assessment.

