**POSTOPERATIVE GLYCAEMIC CONTROL AND THE SURGICAL SITE INFECTION
INCIDENCE AMONG LIVER TRANSPLANTATION RECIPIENTS: RANDOMIZED
CLINICAL TRIAL**

Date: March 13th, 2018.

Version: 1

Author:

[name],

Sao Paulo Registered Nurses Board: Number 265.476

RN, MSc, PhD Candidate at University of São Paulo School of Nursing.

Graduate Program in Adult Health Nursing.

[name].

E-mail: [contact]

[contact]

**POSTOPERATIVE GLYCAEMIC CONTROL AND THE SURGICAL SITE INFECTION
INCIDENCE AMONG LIVER TRANSPLANTATION RECIPIENTS: RANDOMIZED
CLINICAL TRIAL**

ABSTRACT

Context: The hyperglycemia is an important independent risk factor for the Surgical Site Infection (SSI) development among liver transplantation recipients. **Objective:** To evaluate the effects of an intensive postoperative protocol of blood glucose management on the surgical site infection incidence among liver transplantation recipients. **Material and methods:** It is an open-label clinical trial that will be randomized into 2 groups of blood glucose (BG) control: patients will undergo BG control regular in the facility chosen to research development (BG targeted 130-180 mg/dL) and the second one will undergo intensive BG control (BG targeted 80 - 130 mg/dL) until patients are eating at least 50% of a full liquid diet or receiving bolus tube feedings. A computer program will be employed to generate the randomized schedule that will be put into sequentially numbered opaque sealed envelopes by an external expert to research. A finger prick device will be used to measure the blood glucose. A blinded adjudication committee to analyse the primary endpoint SSI will adopt the SSI criteria given by the Centers for Disease Control and Prevention. The research proposal will be registered on ClinicalTrials.gov database. Central tendency and dispersion measures, Pearson's χ^2 test, Fisher's Exact Test, Mann-Whitney, Wilcoxon-Mann-Whitney and survival analysis by Kaplan-Meier estimated and Log-rank test will be used for data analyses. **Expected outcomes:** The results of the study should contribute to establishing better clinical practices on glycemic control in the liver transplantation recipient's postoperative period aiming to reduce SSI incidence and its associated morbidity and mortality.

Descriptors: Glycemia. Surgical Wound Infection. Liver Transplantation. Perioperative Nursing.

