3 METHODS

The Standard Protocol Items: Recommendations for Interventional Trials (SPIRIT) were used to write this methods chapter⁽³⁵⁾.

It is a randomized open-label clinical trial, in other words, the researchers will not try to blind the patients⁽³⁶⁾. Among the research designs, the randomized clinical trial stands out on the observational designs as a result of the greater capacity to demonstrate causality. It particularly stems from a random allocation process that could remove the possibility of effects observed being explained by differences between the use of co-interventions or by other bias in the outcomes analyses^(37, 38).

This study will be performed by two groups, the first one composed of LT recipients who undergo a standard blood glucose protocol, standardized in the facility selected to conduct this research. That protocol consists in a glucose control according to the result of finger prick test and

subcutaneous injection of regular insulin (BG targeted 130 - 180 mg/dL). The second group will be constituted of patients who undergo a strict blood glucose control (BG target 80 - 130 mg/dL) by a continuous intravenous insulin infusion.

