3.12 EVALUATION OF PRIMARY OUTCOME

3.12.1 Through hospital stay

The researcher will evaluate the surgical wound on alternate days before the dressing changes and patient's bathing.

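### SSI case finding comes before blinded adjudication and rests mainly on a researcher whom no section blinds, and neither what is asked nor the point of referral is standardised

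*Protocol*

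**What the plan says.** The protocol's Methods section states: "It is a randomized open-label clinical trial". It explains this by saying that "the researchers will not try to blind the patients", and does not mention the researcher's own blinding. The strict arm is treated "by a continuous intravenous insulin infusion", while the control arm receives subcutaneous insulin (sections 3 and 3.8).

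The one party described as blinded appears in the abstract: "A blinded adjudication committee to analyse the primary endpoint SSI".

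The steps before the committee are these:

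- In hospital (3.12.1): "The researcher will evaluate the surgical wound on alternate days".
- After discharge to day 30 (3.12.2): "The researcher will contact the liver transplant recipient on alternate days by telephone to detect any signs and symptoms of SSI". In addition, "the surgical wound will be evaluated every 7 days during the ambulatory doctor's assessment"; who makes that evaluation is not said.
- On suspicion (3.12.3): when a suspected case meets the CDC criteria, the researcher informs the care team, makes a nursing record entry and photographs the site. The clinical records and image then go to the committee.
- Adjudication (3.13): three experts apply the CDC criteria and decide by simple majority.

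No section describes committee review of patients who were not flagged. The statistical analysis plan does not address ascertainment.

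**The concern.** Blinded adjudication protects the classification of the cases it receives. It does not protect the step before that, in which someone notices a sign, draws out a symptom by telephone and decides that a case is suspected. Here that step falls mainly to a researcher who is probably aware of the arm, in a trial whose stated hypothesis (end of section 1) is that strict control reduces SSI.

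If inspection or questioning were less searching in one arm, infections there would go unflagged and the committee would never see them. The primary comparison would then be distorted before adjudication, and no later analysis could recover the missing events.

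**Working it through.** **Inputs from the documents.** 29 per arm, 40% versus 10%, 80% power, 5% level (3.3); Pearson or Fisher test (3.16 and the SAP); SSI incidence of 9.6% to 35.5% after deceased-donor transplantation (section 1).

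**The plan's own figure.** With unpooled variance and a two-sided 5% level,

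n = (1.960 + 0.842)² × (0.4×0.6 + 0.1×0.9) / 0.30² = 7.85 × 0.33 / 0.09 = 28.8, so 29 per arm and 58 in total. The stated size reproduces.

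**How much a single case can weigh.** With 29 per arm and a and b events, Pearson X² = 58(a − b)² / [(a + b)(58 − a − b)]. The planned 40% control risk is about 12 of 29.

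- 12 versus 6: 58×36 / (18×40) = 2.90, p = 0.089 (Fisher 0.155).
- 12 versus 5: 58×49 / (17×41) = 4.08, p = 0.043 (Fisher 0.082).
- 12 versus 4: Pearson p = 0.019, Fisher p = 0.038.

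One unflagged case can move a borderline result across 0.05 under either test, though not at the same count.

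**Unequal detection with no true effect.** Let π be the true risk in both arms, and s_c and s_s the detection probabilities in control and strict. Observed events are then binomial with risks π·s_c and π·s_s. The chance of a false win for strict control is

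P = Σ Bin(a; 29, π·s_c) × Bin(b; 29, π·s_s), summed over a > b with two-sided p < 0.05.

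The documents give no detection rates. Those below are assumptions: s_c = 95% throughout, s_s varied. The 25% risk is an assumed value inside the cited range; 9.6% and 35.5% are its ends.

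| True risk | Test | s_s = 95% (equal) | 90% | 80% | 70% | 60% |
|---|---|---|---|---|---|---|
| 9.6% | Pearson | 2.6% | 2.9% | 3.8% | 4.9% | 6.3% |
| 9.6% | Fisher | 0.4% | 0.4% | 0.5% | 0.7% | 0.9% |
| 25% | Pearson | 2.4% | 3.1% | 5.0% | 8.1% | 12.6% |
| 25% | Fisher | 1.2% | 1.5% | 2.6% | 4.3% | 7.0% |
| 35.5% | Pearson | 2.3% | 3.2% | 6.0% | 10.7% | 17.8% |
| 35.5% | Fisher | 1.2% | 1.8% | 3.5% | 6.6% | 11.7% |

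The spurious risk difference is π(s_c − s_s). At 25% risk and 90% detection it is 0.25 × 0.05 = 1.25 points, or 29 × 0.0125 = 0.36 of an event per arm. At 70% detection it is 0.25 × 0.25 = 6.25 points, or 1.8 events. If the arms' detection rates were exchanged, the bias would run against strict control by the same amounts.

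**The case against.** The plan has real safeguards. The contact schedule is written without distinction by arm. Section 3.12.3 ties a suspected case to fulfilment of the CDC criteria, so referral is not left to impression alone. Three experts then apply the same criteria, and a weekly wound evaluation after discharge gives a second look. These limit the bias. They do not fix what is looked for or asked at each contact, and no route to the committee is described other than the researcher's referral.

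Several stronger readings are tempting and go beyond the text:

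- *That the researcher is stated to know the arm.* This is an inference. It is a reasonable one, given the open-label design, the differing insulin routes, and the researcher's part in training staff (3.9) and in arranging the protocols with the clinicians (3.7). An independent nurse opens the envelope (3.6), but that protects allocation, not outcome assessment. The infusion is not continued throughout follow-up (3.7.1), so the bedside cue does not last. The same role nevertheless makes the later calls.
- *That the calls are free-form.* Section 3.12.2 does not give their format.
- *That the researcher inspects every wound.* This fits the hospital stay. After discharge the weekly evaluator is unnamed.
- *That even a slight difference in vigilance would produce a false positive.* The table does not bear this out: with 95% against 90% detection the chance rises by less than one percentage point in every row.

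It is also fair to object that a checklist does not blind anyone and that the detection rates are hypothetical. Both objections stand.

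**Conclusion.** The gap is real and worth closing. Case finding comes before blinded adjudication, rests mainly on a researcher whom no section blinds, and is not standardised in content or threshold. A committee that sees only flagged cases cannot restore missed ones.

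The documents do not show that bias will occur, or which arm it would favour. Under the assumed detection rates a slight gap changes little. A moderate gap can matter: at 25% risk, 95% against 70% detection raises the false-win chance from 2.4% to 8.1% (Pearson) or from 1.2% to 4.3% (Fisher). At 9.6% risk the effect is small, and with Fisher the chance stays below 1% throughout. These figures assume no true effect, 29 evaluable patients per arm, and that an unflagged case is never recovered by another route.

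This is a change the plan should make before data collection, because missed events cannot be repaired at analysis. It does not invalidate the design.

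**What to change.** In sections 3.12.1 to 3.12.3:

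1. Complete the same fixed list of CDC signs and symptoms, each marked present or absent, at every inspection and every call for every patient. Let a preset positive answer send the case to the committee for research classification. Leave communication with the care team as 3.12.3 already states it.
2. Record the wound finding at the existing 7-day ambulatory visit on the same form, without stating the arm on it, and let that record send a case to the committee on its own.
3. Report suspected cases and committee-confirmed cases by arm, as a check on unequal thresholds.

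**Cost.** One short form and some protocol wording, with no extra staff or visits. Alternate-day contact over 30 days means about 30 / 2 = 15 forms per patient, plus the weekly ones. The committee will have more cases to read; the documents do not allow that number to be estimated.

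**Limits.** The form reduces discretion but does not blind the researcher, and the ambulatory doctor may also know the arm.

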3.12.3 Evaluation of surgical wound during the hospital stay and after discharge

Facing a suspected SSI case, given the CDC criteria fulfilment, immediately the researcher will communicate with the healthcare team and proceed to register in the nursing records.

After that, the researcher will take a picture of the surgical site, using a digital camera designated for this activity. The clinical records and image will be sent to the adjudication committee for evaluation.

3.13 ADJUDICATION COMMITTEE

Will be formed by three health professional experts on SSI diagnosis and treatment. They will evaluate the classification in SSI or non-SSI only for the research purpose. As a result, these procedures will not affect the implementation or not of SSI treatment by the healthcare team.

In regard to the establishment of adjudicated SSI, the committee will follow the CDC SSI defining criteria and the simple majority will be respected.

3.14 SAFETY MONITORING

For unicentric open-labelled clinical trial, the Data Safety Monitoring Inboard is not necessary, following the National Institutes of Health from United States of America statement⁽⁴¹⁾. However, when 50% of the collected sample is reached the interim analyses will be done by an

independent statistician and a health professional expert, according to the criteria: strongly positive or negative results and futility proposed by Holubkov and cols.⁽⁴²⁾.

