3.3 SAMPLE SIZE

Based on previous studies that showed the reduction of any infection incidence among LT recipients the sample size was calculated on the basis of the primary hypothesis^(16, 40). 58 patients are required to have an 80% chance of detecting, as significant at the 5% level, a decrease in the primary outcome measure from 40% in the control group to 10% in the experimental group. Thus, the sample calculation pointed will need 29 patients allocated in each group.

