3.16 STATISTICAL ANALYSES PLAN

A Microsoft Excel for Mac 2011® database will be constructed. The data will be typed into two different files to ensure accuracy by an automated check. Afterwards, the data will be transferred to the software Statistical Package for the Social Sciences® for Windows® version 22.0.

The results will be computed with a statistician support, following the research objectives and methods. The following tests will be employed:

- Central tendency and dispersion measures.
- The categorical variables will be analysed by the Pearson's χ^2 test or Fisher's exact test.
- The continuous variables will be analysed by the Student t-test or Mann-Whitney.
- Survival analysis by Kaplan-Meier estimate and Log-rank test.
- Visual inspection of residuals from QQ plot will be used to determine the normality.
- The significant level adopted will be $\alpha=0,05$.

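### Does the half-way look, planned without a printed threshold, put the 5% significance level at risk?

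*Protocol*

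**What the plan says.** Protocol 3.14 states that "the Data Safety Monitoring Inboard is not necessary" for a single-centre open-label trial, and then provides for one look: "when 50% of the collected sample is reached the interim analyses will be done". An independent statistician and a health professional expert carry it out. The criteria are "strongly positive or negative results and futility", attributed to a published account of another trial's monitoring board. The section prints no p-value, boundary or futility limit, and it does not use the word stop.

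Protocol 3.3 sizes the trial without reference to a look: "58 patients are required to have an 80% chance of detecting, as significant at the 5% level", for a fall in surgical site infection from 40% to 10%, with 29 patients per arm. Protocol 3.16 and the visible part of the SAP carry the same list of tests. "The categorical variables will be analysed by the" Pearson or Fisher test, with the choice left open. "The significant level adopted will be" 0.05. Neither mentions the look.

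**The concern.** A trial that tests its primary outcome twice, and may claim success either time, spends its false-positive allowance twice. If both tests used 0.05, the overall error would exceed 5%. Here the section that plans the look gives no level, and the sections that give the level do not mention the look. A reader could fear that the threshold for a strong result would be settled after half the data had been seen, in an open-label trial without a monitoring board. The open choice of test adds to this. At the look, 0 of 14 against 4 of 15 infections gives p = 0.037 by Pearson and p = 0.100 by Fisher. At stake would be the claim that a positive result is "as significant at the 5% level".

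**Working it through.** **Inputs.** From 3.3: 40% versus 10%, 80% power, 5% level, 29 per arm. From 3.14: one look at half the sample, so 29 of 58 patients (15 and 14 by arm) and an information fraction of 0.5. From 3.16 and the SAP: final alpha 0.05, Pearson or Fisher. Sidedness is not stated. Two-sided is assumed because it reproduces the plan's figure.

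**The plan's own figure.** With unpooled variance,

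n per arm = (1.960 + 0.842)² × (0.4 × 0.6 + 0.1 × 0.9) / 0.3² = 28.78,

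which rounds up to 29 per arm and 58 in total. This matches.

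**Overall error, normal theory.** Under no difference, the interim and final statistics Z1 and Z2 are bivariate normal with correlation √0.5 = 0.707. Overall error = 1 − P(|Z1| < c1 and |Z2| < 1.960), where c1 is the two-sided critical value for the interim threshold.

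| Interim threshold (two-sided) | Overall error, final test at 0.05 |
|---|---|
| 0.001 | 5.02% |
| 0.005 | 5.19% |
| 0.0052 | 5.20% |
| 0.01 | 5.46% |
| 0.05 | 8.31% |

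**Overall error, exact.** Normal theory is rough at 29 patients, so all binomial outcomes were enumerated: 15 and 14 patients at the look, then 29 and 29 at the end, final test at 0.05, both arms sharing a common infection rate of 25% to 40%.

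| Test at look / at end | Interim 0.001 | Interim 0.005 | Interim 0.01 | Interim 0.05 |
|---|---|---|---|---|
| Pearson / Pearson | 4.6%–4.8% | 4.8%–5.0% | 5.0%–5.2% | 8.1%–8.7% |
| Fisher / Pearson | 4.6%–4.8% | 4.6%–4.8% | 4.9%–5.0% | 6.0%–6.5% |

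Fisher at both analyses stays at or below 4.4%, even with 0.05 used twice.

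**Lower infection rates.** The Protocol's introduction cites a range of 9.6% to 35.5%, so lower rates matter too. At a common rate of 10%, Pearson gives 5.35% both with no look and with a look at 0.001. That small excess belongs to the test and not to the look. Across 10% to 40%, the same enumeration with Pearson at both analyses peaks at 5.55% with an interim threshold of 0.01. With no look at all it peaks at 5.49%.

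**What a strict threshold demands.** A result of 0 of 14 against 4 of 15 passes 0.05 by Pearson. Passing 0.001 takes something like 0 of 14 against 9 of 15. Only the second would ordinarily be called a strong result.

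**Power.** For 40% versus 10%, exact power with Pearson is 77.8% with no look and 77.8% with a look at 0.001. Holding the level at exactly 5% after a 0.001 look would mean a final threshold of 0.0498 instead of 0.05, a negligible difference.

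**The case for a change.** The strongest case on the other side is that the level should not depend on how somebody reads an adjective. The documents print no number, no test for the look and no futility limit. The cited paper may hold a rule, but neither 3.16 nor the visible SAP points to it. If the two people doing the look used an ordinary Pearson test at 0.05, the error would be 8.1% to 8.7% at common rates of 25% to 40%. A look for harm alone at 0.05 would still give 6.7%. Writing the number down would cost two or three sentences and leave the sample size at 58.

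Part of this stands. The number is not transcribed, the look is missing from the analysis section, and the futility criterion has no figure. It is also true that exact power at the end is about 78% with Pearson and 68% with Fisher, but that gap comes from the choice of final test and is the same with or without a look.

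What does not stand is the step from an unprinted number to an unprotected level. Applying 0.05 at half the sample would contradict the plan's requirement of a strong result, for benefit and for harm alike. The decision lies with an independent statistician, and the plan refers that person to a published set of monitoring criteria. A stop for futility can only lower the false-positive rate. Its cost, if acted on, is some power.

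**Conclusion.** The concern does not call for a change. The plan is less explicit than it could be, but on any reading that fits its words the overall two-sided error is 5.0% to 5.5% by normal theory. By exact calculation it is 4.6% to 5.2% at common infection rates of 25% to 40%. Testing at 0.05 at the end, after a strict look, is sound.

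This rests on four assumptions: a two-sided test; a look at about 29 of 58 patients; an interim threshold no looser than 0.01, as the wording implies; and an independent statistician who follows the stated criteria. The content of the cited monitoring paper could not be checked and is not relied on, and the SAP was judged on its visible text only. If an unadjusted 0.05 Pearson test had in fact been used at the look, the conclusion would change, but nothing in the documents suggests it. What remains is a point of documentation.

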3.15 ETHICAL PROCEDURES

University of São Paulo School of Nursing Ethics Committee approved the research proposal (Approval number 2.444.780).

All the legal requirements from resolution Nº 466/2012 of Brazilian National Health Council will be followed⁽⁴³⁾.

The data from donors will be collected from the recipient medical records. In Brazilian Transplant System, the identities of donors are not available in the recipient records as a measure to maintain confidentiality⁽⁴⁴⁾.

3.16 STATISTICAL ANALYSES PLAN

A Microsoft Excel for Mac 2011® database will be constructed. The data will be typed into two different files to ensure accuracy by an automated check. Afterwards, the data will be transferred to the software Statistical Package for the Social Sciences® for Windows® version 22.0.

The results will be computed with a statistician support, following the research objectives and methods. The following tests will be employed:

- Central tendency and dispersion measures.
- The categorical variables will be analysed by the Pearson's χ^2 test or Fisher's exact test.
- The continuous variables will be analysed by the Student t-test or Mann-Whitney.
- Survival analysis by Kaplan-Meier estimate and Log-rank test.
- Visual inspection of residuals from QQ plot will be used to determine the normality.
- The significant level adopted will be $\alpha=0,05$.

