1 INTRODUCTION

The Surgical Site Infections (SSI's) are the most frequent healthcare-associated infections and are an important infectious complication in the postoperative period among liver transplantation (LT) recipients ⁽¹⁻³⁾. SSI incidence among LT recipients, whose allografts were from deceased donors, varied from 9.6% to 35.5% according to a recent literature review⁽⁴⁾. In general surgical procedures, SSI increases the length of stay, morbidity and healthcare costs. Besides that, among LT recipients SSI can raise the risks of the allografts dysfunctions, acute rejections and as a consequence a reduction in the recipient's survival⁽⁵⁻⁷⁾.

There are several risk factors for SSI among LT recipients. There is a relationship among supply sterilization quality, the characteristics of surgical procedure, the operation room environment as well as the allograft's and recipient's conditions and SSI occurrence⁽⁸⁻¹²⁾. In regard to LT recipients, results from previous research highlighted hyperglycemia as an important independent predictor of SSI. Furthermore, regarding this population, it is known from observational studies that LT recipients affected by hyperglycemia are exposed, approximately, to three times the risk of SSI comparatively to LT recipients not exposed⁽¹³⁻¹⁶⁾.

The concern about maintaining normoglycaemia in acute care facilities is not recent; several studies have been done including on clinical and surgical patients from some medical specialities showing the morbidity and mortality reduction throughout the adoption of strict glycaemic control protocols ⁽¹⁷⁻¹⁹⁾.

However, among critical surgical patients the LT recipients are highlighted; since they are exposed to impairment in blood glucose metabolism in the perioperative period as a consequence of an intraoperative acute stress state, blood loss and transfusions, the reperfusion phase, use of glucocorticoids and catecholamines^(20, 21).

Results from previous studies pointed the hyperglycaemia among LT recipient as a frequent complication, 94% of them presented it at least once in the transplantation's postoperative period^(22, 23).

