3.4 SEQUENCE GENERATION AND CONCEALMENT

Participants will be randomly assigned to either standard control or strict control with a 1:1 allocation as a per computer-generated randomisation schedule; the procedure will be performed by an independent statistician.

The randomization schedule will be put into sequentially numbered sealed opaque envelopes by an external expert to research.

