3.6 ALLOCATION

After the patients' acceptance in participating in the research, in the ICU admission, any bedside blood glucose reading equal or superior to 130 mg/dL in the first 24 hours of the postoperative period will determine the LT recipient's allocation in the study. The sealed opaque envelope will be opened by an independent Registered Nurse to allocate the participant in the standard blood glucose control group or strict blood glucose control group.

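### Neither the planned SSI tests nor the randomisation uses the pre-allocation glucose reading that every patient has; adjusting for it may recover a little power and protect against chance imbalance

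*Protocol*

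**What the plan says.** Protocol Section 3.6 (Allocation) states that "any bedside blood glucose reading equal or superior to 130 mg/dL in the first 24 hours of the postoperative period will determine" the recipient's allocation; an independent nurse then opens the envelope. Every randomised patient therefore has a reading that precedes assignment.

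The Introduction says that "results from previous research highlighted hyperglycemia as an important independent predictor of SSI", and puts the risk at about three times that of recipients not exposed. It gives no glucose cut-off for that contrast.

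Section 3.4 says "Participants will be randomly assigned to either standard control or strict control with a 1:1 allocation", from a computer-generated schedule, and names no stratification factor.

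Section 3.16, repeated in the SAP, says "The categorical variables will be analysed by the Pearson's" chi-square test or Fisher's exact test. It adds the t-test or Mann-Whitney for continuous variables, and Kaplan-Meier with the log-rank test. It does not say which test is primary for SSI. Every option listed is unadjusted, and no adjusted sensitivity analysis is planned.

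**The concern.** Treatment cannot have affected a reading taken before the envelope is opened, so adjusting for it is legitimate, and the protocol itself gives a reason to expect it to matter. With 29 patients per arm, the arms can differ by chance in how hyperglycaemic they were at entry. An unadjusted comparison carries that difference into the SSI result.

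Two things are at stake. One is some power, in a trial sized with no margin. The other is a credible answer if the baseline table turns out unbalanced: in an open-label trial, an adjustment chosen after an imbalance has been seen would carry little weight.

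**Working it through.** **Inputs from Section 3.3.** SSI risk 40% versus 10% ("a decrease in the primary outcome measure from 40% in the control group to 10% in the experimental group"), 80% power, "as significant at the 5% level", 29 per group. Two-sided testing and no dropout are assumed, since neither is stated.

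**1. The plan's own figure.** With unpooled variance, n per group = (1.960 + 0.842)² × (0.4×0.6 + 0.1×0.9) / 0.3² = 28.78. That rounds up to 29 per group, 58 in total, which matches the protocol.

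**2. Power of the listed tests.** Full binomial enumeration at 29 per group gives 77.8% for Pearson and 68.1% for Fisher.

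**3. Chance imbalance.** Assume half the patients are in an upper stratum of the reading. The between-arm difference in that share has SD √(0.5×0.5×2/29) = 0.131. By the normal approximation it reaches 10 points in about 45% of trials and 20 points in about 13%; simulation with whole patients gives 14.9% for 20 points.

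If the upper stratum has three times the risk and the overall control risk is 40%, the stratum risks are 0.40/(0.5×3 + 0.5) = 0.20 and 0.60. A 20-point imbalance then shifts the SSI difference by 0.20 × (0.60 − 0.20) = 8 points.

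**4. Type I error under that scenario.** In the 14.9% of trials with an imbalance of 20 points or more, Pearson rejects a true null in 9.6% and the Cochran-Mantel-Haenszel (CMH) test in 4.8%. In the other trials Pearson rejects in 3.7%. Overall: 0.149×9.6 + 0.851×3.7 = 1.43 + 3.15 = 4.6%. At a risk ratio of 2, the conditional rates are 6.6% and 4.9%.

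**5. Power of a stratified test.** Simulation with 29 per arm, unstratified allocation, 40% control risk, strict-arm risk ratio 0.25 and no continuity correction. Pearson is about 77.8% throughout. Entries are CMH minus Pearson, in points.

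| Stratum risk ratio | Upper share 10% | 20% | 30% to 70% |
|---|---|---|---|
| 3 | not run | not run | +4.6 at 30%, +3.4 at 50%, +2.1 at 70% (CMH 82.4, 81.2, 79.9%) |
| 2 | −0.2 | +0.7 | +1.0 to +1.4 (CMH 78.8 to 79.2%) |
| 1.5 | −0.7 | −0.2 | +0.3 at 50% |
| 1 | not run | not run | −0.2 to −0.3 |

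**6. A second method.** Models with the reading as a covariate, 10,000 trials per scenario, marginal risks held at 40% and 10%:
- Two-level reading, risk ratio 3: chi-square 77.6% against linear model 82.0%; logistic likelihood-ratio test 80.6% unadjusted, 83.8% adjusted.
- Two-level reading, risk ratio about 1.9: 78.0% against 79.8%; logistic 80.8% and 81.6%.
- Continuous reading, logistic: odds ratio per SD of 1.35, 80.8% to 80.1%; of 2, 80.1% to 81.5%; of 3, 80.5% to 86.1%. With no association, 80.4% to 79.4%.
- Under the null, the adjusted linear model rejected in 4.7 to 5.3% and the adjusted logistic test in 5.4 to 6.0%.

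**7. Events available.** 29×0.4 + 29×0.1 = 14.5, enough for one or two pre-specified covariates at most.

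**The case against.** The strongest reply is that the threefold risk belongs to a different contrast. The Introduction compares hyperglycaemic recipients with recipients not exposed. In this trial everyone qualifies at 130 mg/dL or more, so the range is truncated. The proposed covariate is also a single finger-prick value; with hourly testing (Section 3.9), a gradual rise could be caught soon after it crosses the threshold. One of the cited studies concerns severe intraoperative hyperglycaemia, which is not the same measurement. This objection stands: the documents give no SSI gradient for the qualifying reading and no distribution of it. The ratio of 3 and the 30% to 70% shares are assumptions.

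A second reply is that a two-level split discards information and that no cut has evidence behind it. The value of 180 mg/dL in the control group's table belongs to an insulin scheme and says nothing about SSI risk. This also stands, and it is why a continuous covariate is offered below.

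A third is that the open choice between Pearson and Fisher matters more: 77.8 − 68.1 = 9.7 points of power. That is true, but it does not remove this point; naming one primary analysis would settle both.

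None of these replies changes the basic facts: the reading precedes allocation, the protocol treats hyperglycaemia as prognostic, and no planned step uses it.

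**Conclusion.** The point holds as a modest matter of efficiency and of protection against chance imbalance. It is a low-cost improvement; the gain is material only if the reading is strongly prognostic within the qualifying range.

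Three stronger readings are tempting, and the documents do not support them:
- A reader might infer that the unadjusted test is biased, or that its result could simply be baseline imbalance. Randomisation already allows for such imbalance. Type I error over all randomisations stayed between 4.4% and 5.2% in every scenario run; the 9.6% applies only to the most unbalanced trials, and only at the assumed ratio of 3.
- A reader might infer that power is certainly lost, or that this reading is the strongest baseline predictor available. Nothing in the documents shows either.
- A reader might infer that randomisation has to be stratified. The gains in the table were obtained with unstratified allocation.

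**What to change.** In Section 3.16 and the SAP, name one primary SSI analysis, adjusted for the qualifying pre-allocation reading and nothing else. Define that reading as the value that triggered allocation. Either form would do:
- a CMH test with a Mantel-Haenszel risk difference, using a cut written down in advance; or
- a model with the continuous reading, reporting a standardised marginal risk difference so that the result does not become a conditional odds ratio. The linear model held its level better than the logistic likelihood-ratio test at this sample size.

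Keep the unadjusted comparison as supporting, and say whether it is Pearson or Fisher. Add one database field for the reading.

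The cost is a few lines of text, one data item and a headline test slightly less simple than a single 2×2 table. If the reading proves uninformative, the power loss is under 1 point for CMH or the linear model, and about 1 point for the logistic test. Separate envelope stacks by reading are optional and not needed for the gain. No aspect of treatment changes.
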